#### 7.2.6 Spirometry

Spirometry will be performed at all scheduled visits except Visit 2 (Randomization). Spirometry at Visit 1 (Screening) will consist of two assessments performed at least 5 days apart during the Screening period. Spirometry at Visit 3 (Week 2) can be performed up to 3 days prior to or after the visit date. Spirometry from Visit 4 (Week 4) to Visit 7 (EOS) can be performed up to 5 days prior to or after the visit date. All spirometry assessments should preferably be performed in the morning at approximately the same time to avoid diurnal variation, and prior to study drug intake.

Spirometry testing will assess FVC and FEV1.

A central reader will provide equipment and a PFT manual with detailed instructions for the procedures, calibration and validation of spirometers. All recorded spirometry values will be transmitted to the centralized provider, and will be reviewed by independent central readers. Quality of the assessments will be evaluated for compliance with ATS/ERS criteria [Miller 2005a, Miller 2005b], and queries may be sent to the sites for clarification. If quality issues are identified, additional training will be provided. The selection of the highest (largest) FEV1 and FVC values to be used for the main endpoint derivations will be validated by the independent central readers prior to being electronically transferred to the sponsor. No data will be reported in the eCRF.

PFT values that trigger study drug discontinuation will be flagged and sent to the sites and the sponsor. Any clinically relevant PFT abnormality detected after signature of informed consent must be reported as an AE or SAE as appropriate [see Section 10] and

must be followed until the value returns to within the normal range or is stable, or until the change is no longer clinically relevant.

The predicted normal values for FEV1 and FVC used to determine the exclusion and discontinuation criteria [see Section 5.1.10.3] will be those as defined by the European Community for Coal and Steel including ethnic group adjustments [Quanjer 1993].

### 7.2.7 Ophthalmological examination

An ophthalmological examination will be performed by an ophthalmologist at any time during the Screening period. Examination at Visit 3 can be performed up to 3 days prior to or after the visit date. Examinations from Visit 4 (Week 4) to Visit 7 (EOS) can be performed up to 5 days prior to or after the visit date.

The ophthalmological examination should include previous eye history and ophthalmic condition, any new or current ophthalmological symptoms, assessment of best corrected visual acuity (Early Treatment Diabetic Retinopathy Study charts), measurement of Goldmann applanation tonometry (recommended, if not available other applanation tonometer allowed), slitlamp examination of the anterior segment, and dilated indirect funduscopy. While the visual acuity and measurement of applanation tonometry exams may be performed by a delegate (e.g., experienced technician, optometrician), the review and interpretation must be performed by the ophthalmologist. Conduct, review, and interpretation of all other ophthalmological exams must be performed by the ophthalmologist.

The purpose of the assessment prior to randomization is to exclude subjects with macular edema or active uveitis from the study and to document a baseline assessment. Assessments at each visit will ensure that any new ophthalmological abnormality is detected and treated at an early stage.

In the eCRF, the date of the ophthalmological examination will be recorded. The results will be documented in the patient charts but will not be reported in the eCRF. The presence/absence of any abnormality (i.e., Yes/No) will be recorded in the eCRF. Clinically relevant findings that are present at the time of signature of informed consent must be recorded on the medical history page of the eCRF. Any clinically relevant ophthalmological abnormalities (including OCT findings [see Section 7.2.8]) detected after signature of informed consent must be reported as an AE or SAE as appropriate [see Section 10] and must be followed until the value returns to within the normal range or is stable, or until the change is no longer clinically relevant.

### 7.2.8 Optical coherence tomography

OCT will be assessed at Visit 1 (Screening) and Visit 6 (EOT). Testing at Visit 1 can be performed at any time during the Screening period. At Visit 6 (EOT), testing may be

performed up to 7 days prior to the visit date but no later than 7 days after the discontinuation of study drug. In addition, unscheduled OCT examination will have to be assessed in the event of visual symptoms or findings suggestive of macular edema according to the ophthalmologist's decision or in case of active uveitis diagnosed during the study. While the OCT exam may be performed by a delegate (e.g., experienced technician, optometrician), the review and interpretation must be performed by the ophthalmologist.

The purpose of the assessment prior to randomization is to exclude subjects with macular edema or active uveitis from the study, and to document a baseline assessment. The site will use the OCT device available locally and must ensure it is working properly. A copy of the calibration certificates done before the day of assessment must be stored as source documents at the site. To the extent that is logistically feasible, the same OCT machine is to be used for each individual subject throughout the study.

In the eCRF, the date of the OCT assessment will be recorded. The results will be documented in the patient charts but will not be reported in the eCRF. The presence/absence of any abnormality (i.e., Yes/No) will be recorded in the eCRF. Any clinically relevant abnormalities detected after signature of informed consent must be reported as an AE or SAE as appropriate [see Section 10].

The OSB will receive all information related to suspected cases of macular edema and will perform a central, blinded review of OCT images and subject's data of suspected cases of macular edema.

### **7.2.9 Chest X-ray**

A CXR will be performed at Visit 1 (Screening) and assessed by the local radiologist in order to exclude any subject with findings suggestive of active or latent TB. Any CXR that had been performed within 3 months prior to Screening can be used; if available, there is no need to repeat CXR at Screening. The report of the CXR must be recorded in the patient file.

### **7.2.10 Test for tuberculosis**

An interferon gamma release assay (QuantiFERON-TB-Gold®) will be performed at Visit 1 (Screening) to screen for active or latent TB. The test will be analyzed and interpreted at the central laboratory and electronically transferred to the eCRF database.

Only subjects with a negative test at Screening and without CXR findings [see Section 7.2.9] at Screening or within the previous 3 months suggestive of active or latent TB can be included in the study. If the test result is positive, subjects must not be included in the study, except if there is documentation that the subject has completed adequate and successful treatment for TB previously. If the test result is inconclusive

(invalid, indeterminate, or borderline), the test may be repeated one time and a negative result must be obtained prior to randomization in order to include the subject. If the result of the repeated test is inconclusive, subjects must not be included in the study.

Details on the performance of the test for TB will be provided in the specific central laboratory manual.

### **7.2.11 Weight and height**

Height will be measured at Visit 1 (Screening). Body weight (in underwear) will be measured at Visit 1 (Screening) and at Visit 6 (EOT).

### **7.2.12 Physical examination**

Complete physical examination (i.e., inspection, percussion, palpation and auscultation) will be performed at Visit 1 (Screening) and Visit 6 (EOT). A symptom-driven, abbreviated physical examination will be performed at all other visits in order to capture assessments needed for the SLEDAI-2K scoring (note: SLEDAI-2K not assessed Visit 3).

The observations should be reported according to body system in the eCRF as either normal or abnormal. If an abnormality is found, it should be specified on the corresponding eCRF page, describing the signs related to the abnormality (e.g., systolic murmur) and not the diagnosis (e.g., mitral valve insufficiency). Clinically relevant findings that are present at study start (i.e., before signing of informed consent) must be recorded on the Medical History or SLE-relevant disease history eCRF page. Physical examination findings made after study start that meet the definition of an AE/SAE [see Sections 10.1.1 and 10.1.2] must be recorded by the principal investigator / treating physician on an AE page of the eCRF and must be reported to Actelion Global Drug Safety department (SAEs only).

## **7.3 Pharmacodynamic and pharmacokinetic assessments**

### **7.3.1 Pharmacodynamic assessments**

The PD marker is total lymphocyte counts, which will be measured as part of the hematology tests [see Section 7.2.1.2].

### **7.3.2 Pharmacokinetic assessments**

PK samples will be collected pre-dose (except EOT and EOS) at all visits from Visit 3 (Week 2) to Visit 7 (EOS).

The date and the time of blood sample collection will be entered in the eCRF. The date and time of the last study treatment dosing before blood draw will be entered in the eCRF.

The site staff will ship the plasma samples to the central laboratory. The central laboratory will ship the samples to the CRO in charge of the PK analysis (see page 3 for contact details).

## 7.4 Disease activity assessments

### 7.4.1 Systemic Lupus Erythematosus Activity Index-2000

The SLEDAI-2K will be assessed by the treating physician at all visits except Visit 3 (Week 2) [see [Appendix 6](#)].

The original SLEDAI is a validated tool for global measure of disease activity introduced in 1985 [[Bombardier 1992](#)]. The SLEDAI-2K is an updated version of the original SLEDAI. It has been validated as a measure of global disease activity and is suitable for use in clinical trials [[Gladman 2002](#)].

The treating physician will perform physical examinations as required [see Section [7.2.12](#)], question the subject on her/his current state and about any potential SLE symptoms and/or manifestation that may have occurred during the past 10 days, and collect all laboratory parameters relevant to the scoring (e.g., protein-to-creatinine ratio, anti-dsDNA titer, dipstick urinalysis). If the dipstick results are positive, urine sample will be further analyzed as clinically indicated (i.e., microscopic analysis of WBC, RBC, casts, and protein quantification).

All relevant data will be entered in the SLEDAI-2K form of the eCRF [see [Appendix 6](#)]. In case of musculoskeletal symptoms, the number of affected joints will be assessed.

#### Important note:

Reduction in WBC count (lymphocytes) is the main PD effect of S1P1 modulators including ACT-334441. Therefore, leukopenia is not assessable in the present study and will be excluded from the SLEDAI-2K scoring.

### 7.4.2 Physician's Global Assessment of disease

The PGA will be assessed by the treating physician at all visits except Visit 3 (Week 2).

The PGA is a visual 100 mm analog scale for assessment of disease activity by the physician ranging from 0 to 3 [see [Appendix 9](#)]. The scale is anchored at 0="None", 1="mild", 2="moderate", 3="severe" [[Petri 2005](#)].

Paper sheets will be provided to clinical sites. The treating physician will rate the overall state of the subject and make a vertical mark on the scale. Only original sheets should be used (i.e., no photocopies). A metric ruler will be used to measure the length between 0 and the vertical mark. The length will be entered into the eCRF.

## 7.5 Quality of Life assessments: 36-Item Short Form Health Survey v2

The SF-36v2™ questionnaire (SF-36v2™ Health Survey® 1996, 2000 by Medical Outcomes Trust and Quality Metric Incorporated) [see [Appendix 10](#)] is used to assess the subject's quality of life. The SF-36v2™ will be completed by the subject at Visit 2 (Randomization) and Visit 6 (EOT). Preferably, the SF-36v2™ questionnaire will be completed by the subject in the morning prior to any other protocol assessment and prior to any other discussion with the investigator or treating physician.

In the SF-36v2™ questionnaire, subjects are instructed to rate their health and capacity to perform daily living activities in eight domains including physical functioning, physical role limitations, bodily pain, general health, vitality, social functioning, emotional role limitations, and mental health during the last 4 weeks. Raw domain scores are determined and transformed to a 0–100 scale as described in the SF-36v2™ manual, and individual domain scores are used to determine the physical and mental component summary scores as described in the SF-36v2™ manual [[Maruish 2011](#)].

The standard SF-36v2™ considering the past 4-week period will be used. A sample of the SF-36v2™ (in English) is provided in [Appendix 10](#). The subject will complete the questionnaire in local language on a validated paper form that will be collected and transcribed in the eCRF.

Actelion has been granted a license agreement for the use of the SF-36v2™ questionnaire.

## 7.6 Biomarker assessments

Serum and ethylenediaminetetraacetic acid (EDTA) plasma samples will be drawn at indicated visits and will be tested by the central laboratory (except lymphocyte subsets, which will be analyzed by the sponsor). Sample collection date will be recorded in the eCRF.

Details of the collection, labeling and shipment of the samples can be found in the laboratory manual provided to the investigator. The tubes and labels for the samples will be provided to the investigator and/or staff by the sponsor or the central laboratory.

### ANA, anti-dsDNA, complement factors and exploratory biomarkers

ANA and anti-dsDNA are a hallmark of SLE, and titers of these autoantibodies have been found to correlate with clinical disease activity and the response to therapy [[Ravirajan 2001](#)]. Low C3 and C4 complement have also been found to correlate with clinical disease activity [[Swaak 1986](#)]. Immunoglobulins may be elevated in SLE patients, and cytokines and other soluble factors have been found to be elevated in serum of SLE patients.

The following biomarkers as indicated below (but not limited to) will be measured at baseline and during the course of study treatment in order to support the SLE diagnosis of involved subjects, to explore their predictive value for treatment response and to explore changes in response to ACT-334441 treatment.

- ANA, anti-dsDNA, complement C3 and C4 (all visits except Visit 3)
- IgM, IgG, IgA, CRP, fibrinogen, and BLYS (Visit 2 and Visits 4 to 7)
- anti-Smith, anti-cardiolipin (IgA, IgG, IgM) , anti-ribosomal P, (Visit 2 only).
- CXCL10 (EDTA-plasma; Visit 2 and Visits 4 to 7)

At Visit 1 (Screening), ANA and/or anti-dsDNA antibody testing should be positive in order to fulfill inclusion criterion 6 [see Section 4.3] unless a documented historical positive testing is available to confirm the subject's eligibility [see Section 4.6.2].

Aliquots of the EDTA plasma samples will be transferred to the sponsor for exploratory analysis of new soluble biomarkers potentially related to SLE and/or S1P1 modulation. Frozen samples will be kept for a maximum duration of 15 years and will be destroyed thereafter.

#### Blood lymphocyte subsets

S1P1 modulators such as ACT-334441 reduce total lymphocyte counts (T and B lymphocytes) in healthy subjects. T and B cells consist of different subsets with potential distinct functions in SLE disease manifestation and progression. Specific subsets of B and T cells such as recently activated short-lived plasma cells are increased in the circulation of SLE patients [Grammer 2003a; Grammer 2003b; Klinman 1991]. Analysis of specific blood lymphocyte subsets may provide a better understanding of the immunomodulatory effect of ACT-334441 in SLE patients.

Blood samples for lymphocyte subset analysis will be taken at Visit 2 (Randomization) , Visit 6 (EOT) and Visist 7 (EOS).

The site staff will ship the blood samples to the central laboratory. The central laboratory will then ship the samples to the sponsor for analysis. B and T cell subsets will be analyzed using a combination of cell surface markers (e.g., CD3, CD4, CD 19, CD 20).

### **7.7 Total blood volume**

The expected total blood volume to be drawn per subject during the entire course of the study is described in Table 3.

**Table 3 Expected total blood volume to be drawn per patient**

Test	Number of tests	Volume per test	Total volume per scheduled study visits
Viral serology at screening (including test confirmation)	1	9 mL	9 mL
Interferon gamma release assay for tuberculosis at screening	1	3 x 1 mL	3 mL
Serum sample at randomization 	1	5 mL	5 mL
Hematology (including coagulation)	7	6 mL	42 mL
Blood chemistry 	7	7.5 mL	52.5 mL
ACT-334441 PK	5	3 mL	15 mL
Complement C3/C4, ANA, anti-ds DNA	6	7.5 mL	45 mL
Exploratory biomarkers (serum)	5	5.5 mL	27.5 mL
Exploratory biomarkers (plasma)	5	5 mL	25 mL
Lymphocyte subsets	3	5 mL	15 mL
Total blood volume drawn at scheduled study visits: 239 mL			

1. To be stored at the central laboratory for potential retrospective analyses of viral serology titers in the event of infections.

2. Includes serum pregnancy.

3. Total blood volume may vary depending on re-test and unscheduled samples

ANA = anti-nuclear antibodies; anti-ds DNA = anti-double-stranded DNA; PK = pharmacokinetic.

## 8 SCHEDULE OF VISITS

To ensure compliance, at each visit, the study personnel must remind WOCBP to use the methods of contraception defined for this study. The reminders must be documented in the hospital chart.

A tabulated summary of all visits and assessments described in the following sections is provided in [Table 1](#). The schedule of visit dates should be established at the time of Screening. It is recommended that subjects adhere to the established visit schedule.

The timepoint for every visit is defined taking as a reference Day 1 (Visit 2), which is the day of randomization.

When scheduling the different assessments for a subject visit, the following should be taken into account:

- The subject must come to the clinic in a fasted condition for all visits, and, when applicable, before administration of study drug.
- The intervals between all visits following Visit 4 (Week 4) and up to EOT (Week 12) visit should not exceed 36 days.
- At Visit 2 (Randomization; Day 1) and on the days of re-initiation of study drug (if applicable), the assessments during the visits will be divided into two parts: before (pre-dose) and after (post-dose) the administration of the study drug, which will be taken at the site.

- At other visits, ECGs, SBP/DBP, spirometry, blood drawings for hematology and biochemistry, along with all other assessments, are to be performed at pre-dose.
- All PK sampling should be done at pre-dose (except EOT and EOS).
- Resting time:
  - When the subject is to go to another department within the hospital for a specific test, sufficient time should be allowed for the subject to rest prior to the examination.
  - Sufficient time between blood drawing and cardiac assessments (i.e., ECGs and/or BP measurement) is to be allowed.

### Re-screening

It is permitted to re-screen subjects once, if the reason for non-eligibility was transient (e.g., abnormal laboratory test, insufficient wash-out period of a forbidden medication, etc.), provided that documented authorization has been received from Actelion. Subjects who were not eligible due to a negative test for varicella zoster antibodies may also be re-screened once after having been vaccinated. All pre-randomization assessments should then be repeated at the time of re-screening (with the exception of CXR evaluation).

A subject who failed the screening for Part A may be re-screened for Part A or screened for Part B.

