#### **Pulmonary**

15. History or presence of severe respiratory disease or pulmonary fibrosis, based on medical history, lung function and chest X-ray (CXR) performed at Screening or within 3 months prior to Screening.
16. Bronchial asthma or chronic obstructive pulmonary disease.
17. Abnormal PFTs: FEV1 or FVC < 70% of predicted normal value; FEV1/FVC ratio < 0.7.

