#### **Infection and infection Risk**

19. Active or latent tuberculosis (TB), as assessed by CXR performed at Screening or within 3 months prior to Screening, and interferon gamma release assay (QuantiFERON-TB-Gold®) at Screening, except if there is documentation that the subject has completed adequate and successful treatment for latent TB infection or TB disease previously.
20. Ongoing known bacterial, viral or fungal infection that is of clinical concern in the judgment of the investigator.
21. A history of any serious infection, defined as life-threatening or requiring i.v. antibiotics or hospitalization, within 30 days prior to Randomization.
22. Hepatitis B, C, congenital or acquired severe immunodeficiency or known human immunodeficiency virus (HIV) infection or positive HIV testing at Screening.
23. Negative antibody test for varicella-zoster virus at Screening.

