### **8.1.1 Visit 1 (Screening)**

Visit 1 will be performed up to 30 days prior to Randomization. Visit 1 date is defined as the date of the first assessment performed for the study (i.e., informed consent signature).

During this visit, subject informed consent will be obtained, and the assessments required for subject eligibility will be performed. These assessments may generally be performed on separate days within the Screening period.

Visit 1 includes:

- After discussing the study with the investigator and after agreeing to participate, the subject must sign the ICF. It is the responsibility of the investigator to obtain written

informed consent prior to any screening assessment. Subjects will be assigned a subject number by the IRT provider, for identification throughout the study. In case of re-screening, the subject number assigned during the first screening procedure will be retained.

- Recording of demographics, medical history, smoking status, and disease history (including documented history of ANA, anti-dsDNA antibodies)
- Review of SLE diagnosis and ACR criteria
- Recording of previous SLE therapies, concomitant medications and background SLE therapies
- Complete physical examination
- Body weight, and height
- SLEDAI-2K and PGA
- CXR (any CXR performed within 90 days prior to Screening can be used). In case of re-screening, CXR does not need to be repeated.
- SBP/DBP (including supine and standing position to assess orthostatic hypotension; see exclusion criterion 13)
- 12-lead ECG
- 24-hour ECG-Holter (starting before 12:00)
- Echocardiography (under the responsibility of the echocardiography specialist)
- Spirometry (under the responsibility of the pulmonary function laboratory technician or expert)
- Ophthalmological examination (under the responsibility of the ophthalmologist)
- OCT (under the responsibility of the ophthalmologist)
- Hematology (including coagulation tests), blood chemistry, and serum pregnancy test for WOCBP
- Viral serology
- TB test
- ANA, anti-dsDNA antibodies, complement C3 and C4
- Urine protein-to-creatinine ratio
- Urinalysis (dipstick)
- Recording of AEs/SAEs: all AEs/SAEs occurring after signing of the ICF are to be reported in the eCRF and on an SAE form, if applicable.

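### Re-screened subjects may skip a repeat chest X-ray with no limit on the film's age, while exclusions 15 and 19 accept only a film from Screening or the 3 months before it

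*Protocol*

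**What the plan says.** The protocol gives two sets of instructions on the chest X-ray.

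**The exemption.** The Re-screening paragraph in Section 8 requires: "All pre-randomization assessments should then be repeated at the time of re-screening (with the exception of CXR evaluation". The Visit 1 list in Section 8.1.1 agrees: "In case of re-screening, CXR does not need to be repeated". In that list the exemption directly follows the ordinary rule that "any CXR performed within 90 days prior to Screening can be used". No maximum interval between first screening and re-screening is given anywhere.

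**The eligibility limit.** Exclusion 15 (severe respiratory disease, pulmonary fibrosis) is judged on "medical history, lung function and chest X-ray (CXR) performed at Screening or within 3 months prior to Screening". Exclusion 19 (active or latent tuberculosis) is judged "as assessed by CXR performed at Screening or within 3 months prior to Screening, and interferon gamma release assay". Section 7.2.9, Section 7.2.10 and footnote 4 of Table 1 carry the same 3-month window. Section 4.4 opens by ruling out a waiver of any exclusion criterion.

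**Related rules.** Re-screening is allowed once. For transient causes it needs documented sponsor authorisation. The reasons named are an abnormal laboratory test, an incomplete wash-out, and a negative varicella antibody test followed by vaccination. On the two parts of the study, the same paragraph says: "A subject who failed the screening for Part A may be re-screened for Part A or screened for Part B".

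**The concern.** The exemption has no time limit, and the criterion that it touches has one that cannot be waived. Once the film has passed 3 months at re-screening, a site can rely on Section 8 and still randomise a subject who does not meet exclusions 15 and 19 as written.

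The film has a job to do in this trial. The study drug lowers circulating lymphocytes. Section 5.1.10.7 notes that tuberculosis in lupus sits mainly in the lung and can be mistaken for pulmonary lupus. Exclusion 19 calls for the film and the interferon gamma release assay together. It also exempts subjects with documented successful treatment for tuberculosis. In those subjects a positive assay does not settle eligibility, so the film carries more of the weight.

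There is also a reporting consequence. SAP Section 6 lists eligibility deviations in randomised subjects among the important protocol deviations. A site could incur one while relying on a permission that the protocol itself grants.

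**Working it through.** The plan states no figure on this point. The check is a comparison of texts followed by day arithmetic.

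**Which Screening counts.** Section 8.1 requires the Screening period to fall within 30 days before Randomization. SAP Section 5.2 lets completed re-screening pages supersede the original ones. For a re-screened subject, the natural reading of *Screening* in exclusions 15 and 19 is therefore the re-screening. If a site reads it as the first screening, the 3-month window no longer constrains the film for that subject.

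**Inputs.** The film may be 0 to 90 days old at the screening visit (Section 8.1.1). Screening to randomisation takes at most 30 days (Section 8.1). Exclusion 18 sets wash-outs to randomisation of 15 days, 30 days, 90 days (belimumab, leflunomide) and 12 months (B cell-depleting agents), ignoring any longer period set by half-life. Assumptions: the last forbidden dose is on the day of first screening, randomisation is on the day the wash-out ends, and the re-screening visit is as early as the 30-day rule allows.

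**Formulas.** With wash-out W in days and film age a at first screening (0 to 90):

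- First-time subject, maximum age at randomisation = 90 + 30 = 120 days.
- Gap from first screening to re-screening = max(W − 30, 0).
- Film age at re-screening = a + gap.
- Film age at randomisation = a + W.

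| Wash-out | Gap (days) | Film age at re-screening (days) | Film age at randomisation (days) |
|---|---|---|---|
| 15 days | 0 | 0 to 90 | 15 to 105 |
| 30 days | 0 | 0 to 90 | 30 to 120 |
| 90 days | 60 | 60 to 150 | 90 to 180 |
| 12 months (365 days) | 335 | 335 to 425 | 365 to 455 |

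The short wash-outs do not by themselves force a breach. After a 90-day wash-out the limit is exceeded when the film was more than 30 days old at first screening, since 60 + 30 = 90. After a 12-month wash-out every film exceeds it. A film already 90 days old at first screening exceeds it at any later re-screening.

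**Does the calendar allow such gaps?** Section 3.1.2 plans 11 months for Part A and 20 months overall, which is 335 and 609 days at 365.25/12 days per month. Subtract 84 days of treatment, then 42 days to End-of-Study or 112 days to the last call. Part A has 335 − 84 − 112 = 139 to 335 − 84 − 42 = 209 days from first screening to last randomisation. The whole study has 609 − 84 − 112 = 413 to 609 − 84 − 42 = 483 days. A 90-day wash-out fits inside Part A. A 12-month gap does not.

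Part B waits for the last Part A subject to reach Week 4. That leaves about 413 − 139 − 28 = 246 days, and 483 − 209 − 28 gives the same. A 12-month gap is therefore permitted by the wording, but on the planned timetable it could arise only between Part A and Part B.

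**The case against.** The strongest reply is that the texts can be followed together. Section 8.1.1 says a repeat is not needed, which does not forbid one. The investigator checks the eligibility criteria at Visit 1 and again before dosing, and no waiver is allowed. A careful site would repeat an expired film. The exemption also sits directly after the 90-day rule, so it could be read as covering only a film that still meets that rule. Re-screening happens once, with sponsor authorisation in the transient cases.

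Much of this stands. A prompt re-screen with a recent film satisfies every passage, and the exemption permits a stale film without ordering one. But the 90-day reading has to be supplied by the reader. The Section 8 paragraph excepts the CXR with no such context. The authorisation sets no film-age test and is not restated for the varicella route.

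Three stronger readings are tempting and are not supported:

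- *Clearance for tuberculosis and lung disease as a whole rests on an old film.* It does not. Everything else is repeated, including the interferon gamma release assay, spirometry, history and physical examination.
- *The live-vaccine rule makes the film about 5 months old at re-screening.* Exclusion 18b counts its 30 days back from Randomization, so those days can run during the re-screening period. The rule adds no month before re-screening.
- *A Part A screen failure could enter Part B on a film more than a year old.* The protocol says such a subject is *screened*, not *re-screened*, for Part B. On the plain wording the ordinary 90-day rule applies. The text does not settle the matter, but that figure cannot be claimed from it.

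**Conclusion.** The point holds in a limited form. The exemption in Section 8 and Section 8.1.1 has no age limit and conflicts with exclusions 15 and 19, Sections 7.2.9 and 7.2.10, and Table 1 footnote 4 whenever the film is more than 3 months old at re-screening. In that case the CXR component of both exclusions is out of date, and only that component.

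Under the stated assumptions the film could be 90 to 180 days old at randomisation after a 90-day wash-out, against at most about 120 days for a first-time subject. The 365 to 455 days after a 12-month wash-out is what the wording permits. On planned durations it could occur only across the two parts, where it is unclear whether the exemption applies. The conclusion also rests on *Screening* meaning the re-screening. On the other reading, the 3-month limit would not bind a re-screened subject's film, and the passages would still need reconciling.

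The documents do not say how many subjects were re-screened; the number affected is probably small. Sample size, power and the pharmacodynamic analysis are not affected. This is a correction worth making, not a threat to the trial's conclusions.

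**What to change.** Reconcile the Re-screening paragraph in Section 8 and the CXR bullet in Section 8.1.1 with exclusions 15 and 19 and Sections 7.2.9 and 7.2.10. The simplest way is to add one clause in both places: the existing film need not be repeated provided that it falls within the protocol's own 3-month window, counted from the re-screening visit. This introduces no new threshold. With it, a film would be at most about 90 days old at re-screening and 90 + 30 = 120 days at randomisation, as for a first-time subject. State also whether the exemption applies to a Part A screen failure who is later screened for Part B.

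The cost is one clause in two places, one clarifying sentence, and a repeat of a scheduled Visit 1 procedure in the few subjects whose film has expired. If enrolment is already complete, as the past tense in SAP Section 2.1 suggests, use the re-screened flag in SAP Section 11.2.2 to find these subjects. Check their film dates and report any film outside the window as an eligibility deviation.
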